4.2 Safety Analysis Set

The Safety Analysis Set is defined as all subjects who receive at least 1 administration of study drug. The Safety Population will be used for all safety analyses in the trial.

5. STATISTICAL CONSIDERATIONS

The numerical data will be summarized with n, mean, SD, min, max, median, Q1, and Q3. Categorical data will be summarized with n and percentages.

There are no multiplicity adjustments in this exploratory Phase 2A study.

All secondary and exploratory endpoints are considered supportive and any statistical tests comparing treatments will be made without adjustment for multiplicity. The resulting p-values from these supportive analyses will be interpreted descriptively as summarizing the weight of evidence for a treatment difference and may suggest avenues for further exploratory analyses or generate formal hypotheses to be tested in future trials.

5.1 Interim Analyses

An interim analysis was to be implemented for planning purposes but was removed from the plan (See Section [5.5](#)).

5.2 Handling of Missing, Unused, and Spurious Data

Regarding missing data in AE records:

- Handling of unknown causality assessment:
 - If a subject experiences an AE with a missing causality assessment, the relationship of the AE will be counted as “related”.
- Handling of unknown toxicity grades:
 - If a subject experiences more than one AE categorized under the same preferred term, the subject will be counted under the most severe toxicity grade reported for that AE.
 - If a subject experiences an AE and the toxicity grade was not provided, the toxicity grade of this AE should be counted as “unknown”. A row or column labelled “Unknown” should be inserted for those AEs in tables where AEs are summarized by toxicity grade.

For lab values that are above or below the limit of quantitation and are reported as “<” or “>” the assay limit, the assay limit will be used for calculation of summary statistics, except for PK parameters which will be specified in a separate document.

5.3 Definition of Baseline

Baseline will be defined as the last assessment before the date and time of first administration (C1D1) of imalumab or SoC. For subjects who have not received any study drug, the baseline will be the last assessment performed at Screening, Baseline, or C1D1.

If more than one baseline scan is recorded then measurements from the one that is closest and prior to the date of randomization will be used to define the baseline.

5.4 Definition of Treatment Groups

Data will be presented for the cohorts in Part 1 and Part 2 of this study which are listed in [Table 1](#).

The dose of imalumab selected for Part 2 is 10 mg/kg. Subjects from Part 1 and Part 2 who received the 10 mg/kg dose will be combined for some analyses of safety and efficacy. The Part 1 and 2 analyses will indicate that subjects in 10 mg/kg cohorts in Part 1 will be combined with the Part 2 cohorts that received the same treatment.

Data from the cohorts receiving 7.5 mg/kg imalumab in Part 1 will not be included in the integrated Part 1 and 2 analyses.

Table 1: Combination and Pooled Treatment Groups

Study Part	Study Cohort	Integrated Treatment Group
Part 1	Imalumab 7.5 mg/kg + 5-FU/LV	
Part 1	Imalumab 7.5 mg/kg + Panitumumab	
Part 1	Imalumab 10.0 mg/kg + 5-	Imalumab 10.0 mg/kg + 5-

	FU/LV	FU/LV
Part 2	Imalumab 10.0 mg/kg + 5-FU/LV	
Part 1	Imalumab 10.0 mg/kg + Panitumumab	Imalumab 10.0 mg/kg + Panitumumab
Part 2	Imalumab 10.0 mg/kg + Panitumumab	
Part 2	SoC Mutated	SoC Mutated
Part 2	SoC Wildtype	SoC Wildtype

5.5 Changes from the Planned Statistical Analysis in Protocol

In the protocol	In the SAP	Justification
An interim analysis will be implemented for planning purposes when 33 PFS events have been observed.	An interim analysis will not be performed	The interval between observing 33 PFS events and observing the 48 PFS events needed for final analysis was short. Therefore, interim analysis was not performed.
The primary efficacy outcome measure is PFS (Part 2), defined as time between treatment initiation and tumor progression (per RECIST v1.1) or death from any cause (see Section 8.4.1).	The PFS will be defined as time between randomization and tumor progression (per RECIST v1.1) or death from any cause (see Section 8.4.1).	To align the starting point of PFS and OS.

6. STUDY SUBJECTS

6.1 Disposition of Subjects

A summary of patient enrollment will display the number of patients who were screened, screen failures, randomized and treated. Subject disposition will summarize the number (%) of subjects that comprised each analysis population. A listing of subject disposition, including analysis populations, will be created.

6.2 Demographic and Baseline Characteristics

The following baseline data will be summarized and listed for the FAS and Safety Analysis Set: age (years), sex, race, ethnicity, country, Eastern Cooperative Oncology Group (ECOG) performance status, left ventricular ejection fraction (LVEF), height (cm), weight (kg), and BMI (kg/m²). Demographics and baseline characteristics will be summarized for study cohort and integrated treatment group.

6.3 Medical History

Disease history will be summarized for the Safety Analysis Set for study cohort and integrated treatment groups. Disease history will include type of colorectal cancer, stage at initial diagnosis, histological subtypes, time since primary diagnosis (years), diagnosis confirmation type (histologically or cytologically), KRAS/NRAS status, TNM staging at informed consent, and sites of distant metastatic disease.

Duration from initial diagnosis (years) diagnosis will be calculated at the date of informed consent using the following formula:

- Duration from initial diagnosis (years): (Date informed consent signed – Date of initial diagnosis) / 365.25.

Medical history will be summarized for the Safety Analysis Set for study cohort.

Medical conditions collected will be mapped by the Dictionary for Regulatory Activities (MedDRA) and will be summarized by system organ class (SOC) and preferred term.

For summary tables, a subject will be counted only once per body system and preferred term. Disease and medical history will be included in data listings.

6.4 Prior Therapies and Medications

Prior therapies and medications include prior cancer-related surgeries, radiotherapies, and medications as well as other general medications taken prior to the first dose in Cycle 1. Prior cancer-related surgeries, radiotherapies, and medications are collected on

specifically-designed CRFs. Other prior medications will be recorded on the concomitant medications eCRF and coded using the WHO Drug Dictionary version September 2015. Medication start dates will be used to identify which medications entered on the concomitant medications eCRF could be considered as prior medications. Prior cancer-related surgeries, radiotherapies, and medications will be summarized for the Safety Analysis Set for study cohort and integrated treatment group.

Prior medications will be tabulated by WHO Preferred Name for the Full Analysis Set and will be included in a general concomitant medication listing that will identify prior medications. The number and percent of subjects who experienced prior cancer-related surgeries and radiotherapies will be tabulated along with other cancer-related medications tabulated by WHO Preferred Name. Prior medications will be summarized for the Safety Analysis Set for study cohort and integrated treatment group. Prior cancer-related surgeries, radiotherapies, and medications will also be included in data listings.

6.5 Concomitant Medications

Concomitant medications are defined as medications taken after the start of study treatments. Concomitant medications will be recorded on the eCRF and coded using the WHO Drug Dictionary version September 2015. Medication start and end dates will be used to identify which medications entered on the concomitant medications eCRF could be considered as concomitant medications. Concomitant medications will be summarized for the Safety Analysis Set for study cohorts and integrated treatment groups. All concomitant medications will be included in by-subject data listings.

6.6 Protocol Deviations

A protocol deviation summary will be provided. The number and percent of subjects with protocol deviations will be summarized by severity and category for the Part 1 and 2 safety analysis set by study cohort. The protocol deviation categories are:

1. Informed Consent Criteria
2. Eligibility and Entry Criteria
3. Concomitant Medication Criteria
4. Laboratory Assessment Criteria
5. Study Procedures Criteria
6. Serious Adverse Event Criteria
7. Randomization Criteria
8. Visit Schedule Criteria
9. IP Compliance
10. Efficacy Criteria
11. Administrative Criteria

12. Source Document Criteria
13. Regulatory or Ethics Approvals Criteria
14. Other Criteria

All protocol deviations will be included in by-subject data listings.

7. EFFICACY EVALUATION

7.1 Analysis of Primary Efficacy Outcome Measure

7.1.1 Derivation of Primary Efficacy Outcome Measure

The revised RECIST guidelines ([Eisenhauer et al., 2009](#)) will be used to determine disease progression. Date of disease progression is the earliest date of the imaging method to determine disease progression.

For an individual subject, the imaging method used to measure tumor burden at baseline should be used for each future tumor assessment. Baseline tumor measurements and identification of target lesions may be based on imaging obtained within 28 days prior to screening. Scheduled tumor response assessments must be interpreted prior to the start of the next treatment cycle.

Date of Progression will be derived as follows:

1. For progression based on new lesion(s), the date of progression is the first scan date on which the new lesion is detected.
2. For progression based on target lesions, , the date of progression is the date of the initial scan of target lesions showing >20% increase in the sum of diameters of target lesions;
3. For progression based on non-target lesions, the date of progression is the date of the first scan that indicated unequivocal progressive disease of existing non-target lesions.

The date of progression will be the earliest date among dates described above.

For tumor response evaluation from assessments on which multiple scans are done on different dates and no evidence of progression is indicated, the latest date of all scans will be considered as the evaluation date showing no evidence of progression for that assessment. In cases where one or more lesions (target or non-target lesions identified at baseline) do not have an assessment at a given post-baseline evaluation, the assessment

for tumor response for that visit will be considered “not evaluable (NE)” unless disease progression is noted.

PFS is defined as the time between randomization and tumor progression (per RECIST v1.1 criteria) or death from any cause, with censoring of subjects who are lost to follow-up or withdraw consent.

This will be regardless of whether the subject receives another anti-cancer therapy prior to progression. Subjects who have not progressed or died at the time of analysis will be censored at the time of the latest date of assessment from their last evaluable RECIST assessment. However, if the subject progresses or dies after two or more missed tumor assessments, the subject will be censored at the time of the latest evaluable RECIST assessment. If the subject has no evaluable visits or does not have baseline data they will be censored at 1 day unless they die within two visits of baseline. For this study, the exact time period that identifies that two tumor assessments have been missed will be defined as twice the protocol-defined time between scans + the protocol allowed visit window. RECIST assessments are scheduled to occur every other cycle, ie, every 8 weeks \pm 1 week. If tumor scans indicate progression or the subject dies more than $2*9$ weeks=18 weeks (126 days) after the previous tumor assessment, the subject will be censored on the date of the assessment prior to progression or death.

Table 2 below specifies the date of disease progression or censoring rules that will be carried out for the PFS analysis:

Table 2: Date of Progression or Censoring for Progression-free Survival

Situation	Date of Disease Progression or Censoring	Outcome
Alive with no post-baseline assessments for tumor response	Treatment start date	Censored
Disease progression or death after two or more consecutive missed tumor response assessments	Date of last scan for tumor assessment showing no evidence of disease progression that is before the first missed visit.	Censored
Not known to have progressed or died according to data in the database as of data-cut-off	Date of last scan for tumor assessment showing no evidence of disease progression	Censored
Withdrawal from the study or loss to follow-up	Date of last scan for tumor assessment prior to withdrawal or loss to follow-up	Censored
Disease progression reported on multiple response assessments	Earliest Date of Progression as defined in this Section	Progressed
Death without Disease Progression	Date of death	Progressed

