4. ANALYSIS SETS

4.1 Full Analysis Set

The Full Analysis Set (FAS) will serve as the population for the analyses of efficacy data in the trial. The FAS will include all subjects who 1) received at least 1 administration of study drug, and 2) have 1 post-baseline tumor response assessment based on RECIST v1.1, or died within 18 weeks of the start of treatment.

The proposed derivation of PFS (Section 7.1.1) indicates that subjects who miss 2 planned tumor assessments will be censored at the last tumor assessment before the

missed assessments. For this study, the exact time period that identifies that 2 tumor assessments have been missed will be defined as twice the protocol-defined time between scans (8 weeks) + the protocol allowed visit window (1 week) (ie, $2 * 8 + 1 = 18$ weeks).

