7.2.1.2 Overall Response Rate

Tumor response will be assessed by the investigator based on the revised RECIST guidelines (Version 1.1) at each radiographic assessment. Radiological exams are required every 8 weeks (± 7 days) starting from date of randomization without delays for toxicity until protocol-defined disease progression is noted. Results based upon scans performed after start of new anti-cancer therapy will be excluded when calculating the best overall response. Objective response rate will be defined as the proportion of subjects with a complete response (CR) or a partial response (PR) per RECIST based upon the best response as assessed by the investigator; confirmation of response is not required. Clinical benefit rate (CBR) will be defined as the proportion of subjects with a complete response (CR), a partial response (PR), or stable disease (SD) per RECIST based upon the best response as assessed by the investigator. The analysis of ORR and CBR will be performed using Fisher's exact test to compare the relative rate of subjects with an objective response in the treatment groups without stratification. Clopper-Pearson exact 2-sided 95% confidence limits will be calculated for the proportion of subjects with ORR in each arm.

Since the presence of measurable disease is an inclusion criterion, the denominator for the rate will be the number of subjects in the FAS. In addition to representing ORR and CBR, the best overall response (BOR) using response categories CR, PR, SD, progressive disease (PD), and not evaluable (NE) will be tabulated. The proportion of subjects in each response category will be calculated for the study cohorts and the integrated treatment groups.

Subjects who do not have any post-baseline tumor assessment will be counted under the category Not Evaluable (NE).

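### The SAP 7.1.1 126-day missed-scan rule does not exclude the baseline scan, so a week-16 progression after one missed scan can be censored before randomisation

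*SAP*

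**What the plan says.** SAP 7.1.1 measures PFS from randomisation. It states that "the exact time period that identifies that two tumor assessments have been missed will be defined as twice the protocol-defined time between scans" plus the visit window, and works this out as 18 weeks. For an event beyond that limit the rule reads: "126 days) after the previous tumor assessment, the subject will be censored on the date of the assessment prior to progression or death".

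Table 2 in the same section describes the situation by a count of scans: "Disease progression or death after two or more consecutive missed tumor response assessments". It sets the censoring date as "Date of last scan for tumor assessment showing no evidence of disease progression that is before the first missed visit". A separate sentence deals with subjects who have no evaluable visits or no baseline data: they are "censored at 1 day unless they die within two visits of baseline".

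Three other places bear on the starting point:
- SAP 4.1 repeats that "subjects who miss 2 planned tumor assessments will be censored at the last tumor assessment" before the misses. It admits to the FAS a subject without a post-baseline scan who "or died within 18 weeks of the start of treatment".
- SAP 7.2.1.2 sets the scan calendar at every 8 weeks, plus or minus 7 days, "starting from date of randomization without delays for toxicity until protocol-defined disease progression is noted".
- Protocol 11.2 accepts a baseline scan up to 28 days before C1D1. Protocol 10.3.2 places randomisation at the C1D1 predose visit.

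**The concern.** The limit is meant to separate one missed scan from two. That requires the gap to run between two points on the 8-week calendar. The baseline scan is not on that calendar, because it may precede randomisation by up to four weeks. If it is the only earlier assessment, its age is added to the gap, and one missed scan can look like two. The rule then also places the censoring date before time zero.

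This is the derivation of the primary endpoint in an open-label trial. A documented progression could become a record with negative time, which the programmer must drop, reset or reclassify without a written rule.

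**Working it through.** **Inputs.**
- Scan interval 56 days, window ±7 days (SAP 7.1.1 and 7.2.1.2).
- Censoring if the gap exceeds 126 days (SAP 7.1.1).
- Baseline scan 1 to 28 days before C1D1 (protocol 11.2). SAP 7.1.1 instead allows 28 days before screening. Screening is Days -28 to -1, so that wording reaches about 56 days before C1D1.
- Randomisation at C1D1 predose, taken as day 0.
- Week-16 scan: day 112 counted from randomisation (SAP 7.2.1.2), window 105-119; or Cycle 4 Day 28 (protocol 10.3.3.7), which is 111 days after C1D1, window 104-118.

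**1. The plan's own figure.** 2 × (8 + 1) weeks × 7 = 126 days, which reproduces SAP 7.1.1. The expression in SAP 4.1, 2 × 8 + 1, equals 17 weeks or 119 days, not 18 weeks. The sentence defining the period in 7.1.1 has the same slip if the window is added only once.

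**2. Between post-baseline scans.** Gap = 56 × (missed scans + 1) ± 14.
- One miss: 112 ± 14 = 98 to 126 days, never above 126.
- Two misses: 168 ± 14 = 154 to 182 days, always above 126.

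So 126 days separates the two cases exactly. A limit of 119 would not, since one miss can reach 126.

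**3. From the baseline scan.** Let L be the days from the baseline scan to C1D1, and d the day of the week-16 scan. After one miss (week 8), gap = L + d, and the rule censors if L + d > 126.

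| Week-16 scan | Day 112 anchor | Cycle 4 Day 28 anchor |
|---|---|---|
| 7 days early | L > 126 - 105 = 21 | L > 126 - 104 = 22 |
| On schedule | L > 126 - 112 = 14 | L > 126 - 111 = 15 |
| 7 days late | L > 126 - 119 = 7 | L > 126 - 118 = 8 |

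All these thresholds lie within the permitted 28 days. With L = 28 and d = 112 the gap is 140 days, and the censoring time is -28 days. At the 56-day reach of the SAP wording, the Cycle 4 Day 28 gap is 56 + 111 = 167 days.

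A progression at week 8 is not affected: 28 + 63 = 91 days.

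**4. Do other rules catch this subject?** The day-1 sentence needs no evaluable visits or no baseline data. The Table 2 row that censors at treatment start needs no post-baseline assessment. This subject has a baseline scan and an evaluable week-16 scan, so neither applies. On its plain wording, Table 2 would count an event, because only one assessment was missed.

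**5. Counting from randomisation instead.** One miss gives 105 to 119 days (104 to 118 on the other anchor), so the event is kept. Two misses give 161 to 175 (160 to 174), so the subject is still censored. This is the separation that Table 2 describes.

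**6. Two misses, then progression at week 24.** From the baseline scan the gap is 161 + 1 = 162 to 175 + 28 = 203 days. The subject is censored at the baseline scan under the text and under Table 2, again at a negative time. Whether that record is dropped, set to 0 or set to day 1, it is in no risk set after day 1, so the log-rank result does not change.

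**7. Deaths without a post-baseline scan.** Counted from a scan 28 days before C1D1, the limit ends at day 126 - 28 = 98. The FAS window runs to day 126 from start of treatment. The two-visits exception probably governs these deaths, but it gives no number of days.

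**The case against.** The SAP nowhere says that the 126 days run from the baseline scan. The sentence before the rule describes the on-treatment scan series, so the authors may well have had only post-baseline scans in mind. This stands: the baseline starting point is a literal consequence of the wording, not an instruction. But the SAP calls the period exact and names no other starting point.

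A reader might infer that the text and Table 2 flatly contradict each other. That holds only on Table 2's plain wording. SAP 7.1.1 also says that the 126-day period is what identifies two missed assessments. If Table 2 is read through that definition, the contradiction disappears, but the one-miss subject is then wrongly censored under both.

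The reach is narrow. It needs a missed first scan, no other evaluable scan before week 16, progression first seen there, and an older baseline scan. Scans at the end-of-study and safety follow-up visits, due when more than 4 weeks have passed, reduce it further. The second sensitivity analysis in SAP 7.3 counts as events subjects censored for two missed assessments. It may restore this subject, depending on the same ambiguity, but it leaves the primary log-rank test as it was. The study is also exploratory, with a one-sided alpha of 0.15. These points limit the consequence but do not supply the missing rule.

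**Conclusion.** The concern holds. Followed literally, SAP 7.1.1 can turn a valid week-16 progression after one missed scan into a censored record dated before randomisation. The trigger is a baseline scan more than about 14 to 15 days before C1D1 at the scheduled visit, or more than about 7 to 22 days across the scan window and the two scan-day anchors. This assumes randomisation at C1D1 and the baseline-scan limit in protocol 11.2; the wording in SAP 7.1.1 would widen the range.

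The number of subjects affected cannot be computed, because the documents give no missed-scan rate and no distribution of baseline-scan age. It is probably small. One such record is 1/48 = 2.1% of the planned events.

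A reader might infer that about half of such subjects would be censored, since 210 of the 420 permitted combinations of 28 baseline ages and 15 scan days exceed the limit (195 on the Cycle 4 Day 28 anchor). That is a count of calendar combinations, not a rate. A reader might also infer a loss of power. The documents do not support this: they do not say whether the 48-event cut-off is counted before or after this censoring. The week-24 case is a defect in the dates only.

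**What to change.** Add to SAP 7.1.1 and Table 2:

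> If there is no evaluable post-baseline scan before the event, the 126 days are counted from randomisation. Progression or death within that period is an event; later events are censored at day 1. No subject is censored before day 1.

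Then:
- State that the two-visits exception for deaths means the same 126 days.
- In SAP 4.1 and 7.1.1, write the period as 2 × (8 + 1) = 18 weeks (126 days), and change the defining sentence to twice the sum of interval and window.
- In SAP 7.1.1, replace the baseline-imaging limit tied to screening with the protocol 11.2 limit tied to C1D1.
- Leave the FAS death window anchored at start of treatment, as in protocol 13.2.

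The cost is a few sentences in the SAP and a few lines in the PFS derivation program. No new data, visits or scans are needed.

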9.3 Withdrawal and Discontinuation

Any subject may voluntarily withdraw (ie, reduce the degree of participation in the study) consent for continued participation and data collection. The reason for withdrawal will be recorded on the End of Study CRF. Assessments to be performed at the termination visit (including in cases of withdraw or discontinuation) are described in Section 10.3.3.8 and Section 20.2.

Discontinuation (ie, complete withdrawal from study participation) may be due to dropout (ie, active discontinuation by subject) or loss to follow-up (ie, discontinuation by subject without notice or action). Additionally, the investigator and sponsor have the discretion to discontinue any subject from the study if, in their judgment, continued participation would pose an unacceptable risk for the subject.

Subjects also will be withdrawn from treatment or discontinued from further study participation for the following reasons:

- Disease progression according to RECIST v1.1
- Clinical progression due to the subject's underlying malignancy
- Excessive toxicity
- Intercurrent illness unrelated to the subject's underlying malignancy that prevents further participation
- The subject becomes pregnant. IP exposure will be discontinued. Attempts will be made to follow the subject through completion of the pregnancy and up to 1 year post-delivery, if feasible. The investigator will record a narrative description of the course of the pregnancy and its outcome.
- The subject begins lactating. IP exposure will be discontinued. The investigator will record a narrative description of the course of the baby's development.
- Participation in another clinical study involving an investigational product during the course of the study.
- Protocol non-compliance
- Subject withdrawal of consent
- Study closure or termination by the sponsor
- Use of prohibited therapies (see protocol Section 10.4)

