10.3.3.10 Survival Follow-Up (Post Therapy)

For subjects who have stopped study drug or have documented disease progression, post-study telephone calls to assess OS will be made by site staff every 3 months.

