2.3 Sample Size and Power Calculations

The final sample size of Part 1 (Safety Run-in) is dependent on the pre-stated rules for dose escalation. In Part 1, the sample size for each dosing regimen (ie, imalumab + 5-FU/LV and imalumab + panitumumab) is expected to be between 6 and 12 subjects (ie, 3 to 6 subjects at each 7.5 mg/kg and 10 mg/kg imalumab dose level). Non-evaluable subjects will be replaced to meet study objectives.

The sample size of Part 2 (Exploratory Phase 2a) is estimated to be a total of 66 subjects. Assuming that the median PFS is 2.4 months in the control arm and 4.25 months in the experimental arm (a constant hazard ratio 0.565), and using a one-sided log-rank test with α of 0.15 and β of 0.20 with a drop-out rate of 20% at 6 months, 48 PFS events are needed. With an enrollment ratio of 2:1, and taking into account the time for accrual of 1 year and an additional follow-up period of 6 months after the last subject is enrolled, the sample size needed is approximately 22 subjects in each of the 2 imalumab-containing treatment arms (imalumab + panitumumab and imalumab + 5-FU/LV) and in the control arm (SoC).

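### SAP Table 2 places a subject who leaves the study without progression and then dies under two PFS rows with opposite outcomes, and states no precedence

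*SAP*

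**What the plan says.** SAP 7.1.1 sets out the PFS censoring rules twice, in running text and in Table 2.

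- **Running text.** "Subjects who have not progressed or died at the time of analysis will be censored", at the last evaluable RECIST assessment. A known death is censored only if it falls more than 18 weeks (126 days) after the previous assessment, apart from a separate rule for subjects with no evaluable visit or no baseline data.
- **Table 2, withdrawal row.** A subject who leaves the study or is lost is censored at "Date of last scan for tumor assessment prior to withdrawal or loss to follow-up". The row does not ask whether progression or death was recorded later.
- **Table 2, death row.** "Death without Disease Progression" is an event at the date of death.
- **Table 2, no-event row.** A subject with neither progression nor death in the database at cut-off is censored at the last scan without progression.

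No order of precedence among the rows is given. The PFS definition (Protocol 8.4.1; SAP 3.1.1 and 7.1.1) names only two grounds for censoring, loss to follow-up and withdrawn consent. The Table 2 row covers any withdrawal from the study.

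Protocol 9.3 uses withdrawal for a reduced degree of participation and discontinuation for complete exit. It then runs the two together: "Subjects also will be withdrawn from treatment or discontinued from further study participation for the following reasons", with clinical progression, toxicity, intercurrent illness and non-compliance among the reasons. Under Protocol 10.3.3.10, once study drug has stopped or progression is documented, "post-study telephone calls to assess OS will be made by site staff every 3 months".

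**The concern.** A subject who leaves without RECIST progression and is recorded as dead a few weeks later meets both the withdrawal row and the death row. One gives a censored time at an earlier scan, the other an event. Such deaths can be in the database, because they are collected for OS.

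If the withdrawal row is applied, the censoring is informative: subjects who leave while deteriorating and then die are treated as if their later risk were that of subjects still under observation. That lengthens PFS in whichever arm has more of them. The trial is open-label and its control may be best supportive care, so exits could differ by arm. With no precedence fixed, the choice could also be made when outcomes are already known.

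The three PFS sensitivity analyses in SAP 7.3 do not cover this. The first adds censoring at new anti-cancer therapy, the second restores only events censored for two missed assessments, and the third adds Part 1 subjects.

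**Working it through.** **1. The rules applied to one illustrative subject.** Last scan without progression at week 8, leaves at week 10, recorded death at week 14. The death is 14 − 8 = 6 weeks after the last assessment, inside the 18-week limit.

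| Rule | Result |
|---|---|
| Running text, SAP 7.1.1 | Event, week 14 |
| Table 2, death row | Event, week 14 |
| Table 2, withdrawal row | Censored, week 8 |

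**2. What the withdrawal row adds.** Leavers with no recorded event are already censored at the last scan by the no-event row. The withdrawal row can therefore change an event/censored outcome only for a leaver who does have a later recorded event.

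**3. The plan's own figures.** Inputs from SAP 2.3: "Assuming that the median PFS is 2.4 months in the control arm and 4.25 months in the experimental arm"; "a constant hazard ratio 0.565"; "using a one-sided log-rank test with α of 0.15 and β of 0.20 with a drop-out rate of 20% at 6 months"; 2:1 allocation; 12 months accrual plus 6 months follow-up.

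- Events (Schoenfeld) = (1.036 + 0.842)² / [(1/3)(2/3)(ln 0.565)²] = 48.7. The plan says 48, at which power is 0.796.
- With exponential PFS and drop-out, about 63 subjects give 48 events and about 64 give 48.7 to 49. The next 2:1 multiple is 66, so the plan's figures reproduce.

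**4. Subjects leaving before an event.** Monthly hazards:

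- Drop-out η = −ln(0.8)/6 = 0.0372
- PFS control λ = ln 2/2.4 = 0.2888; experimental λ = ln 2/4.25 = 0.1631

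With h = λ + η and uniform accrual, P(leave before event) = (η/h) × [1 − (e^(−6h) − e^(−18h))/(12h)].

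- Control: 0.110 × 22 = 2.4
- Experimental: 0.165 × 44 = 7.2
- Total: about 9.7 of 66. Expected events by month 18 are 50.6.

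**5. Outcomes that depend on the row.** The documents do not say what share of leavers would have a recorded death within 18 weeks. Assuming 25% to 75%:

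- 0.25 × 9.7 = 2.4 and 0.75 × 9.7 = 7.2, so about 2 to 7 subjects
- 2.4/48 = 5% and 7.2/48 = 15%

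**6. Hazard ratio.** An illustrative simulation used 2000 runs per scenario, the same 25% to 75% shares, death within 2 months of withdrawal, a fixed 18-month cut and a one-step HR estimate. The one-step estimate lies below 0.565 even with equal exits, so only the contrast between the two columns is informative. Withdrawal rates are at 6 months; the unequal ones are assumptions.

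| True HR | Withdrawal, control / experimental | Deaths censored | Deaths counted |
|---|---|---|---|
| 0.565 | 20% / 20% | 0.50–0.51 | 0.52–0.54 |
| 0.565 | 10% / 25% | 0.52–0.53 | 0.55–0.59 |
| 0.565 | 25% / 10% | 0.48–0.49 | 0.48–0.49 |
| 1 | 25% / 10% | 0.94–0.96 | 0.92–0.95 |

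More exits on imalumab make censoring flatter imalumab. More exits on control leave the HR unchanged or move it slightly against imalumab.

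**7. Event count.** If 2 or 7 events were lost from 48 and not replaced, power would fall from 0.796 to 0.785 (46 events) or about 0.75 (41 events). This is a bound only, because the Part 2 cut-off waits for 48 events (Protocol 13.4.1 and 13.5).

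**The case against.** The best defence is that SAP 7.1.1 should be read as a whole. The text introducing Table 2 confines general censoring to subjects who have neither progressed nor died, so a known death within 18 weeks is an event and the withdrawal row is for leavers with nothing further on record. That is probably what was meant. It is not stated, however, and on that reading the row duplicates the no-event row, so a programmer who gives it separate effect will censor deaths.

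It is also fair to say that the overlap may be small. Stopping treatment is not by itself leaving the study, since Protocol 9.3 separates the two with an *or* and survival calls continue after study drug stops. Subjects who withdraw consent or are lost will often have no later death data. Protocol 10.3.3.8, 10.3.3.9 and 11.2 ask for a scan at the End of Study and Safety Follow-up visits when the last was more than 4 weeks earlier, so some deteriorating subjects will have progression documented and count as events. All of this stands and limits the size, which the documents do not fix.

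A reader might infer more, and the documents do not support it:

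- *That Table 2 censors everyone who leaves.* Progression on a scan before exit remains an event under the earliest-progression row.
- *That the SAP expressly overrides recorded deaths.* The row is silent on later deaths; the defect is an overlap.
- *That the trial would end short of 48 events.* The cut-off is event-driven, so lost events delay the analysis.
- *That the HR is biased by a known amount or towards a known arm.* No arm-specific exit rates are given.

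**Conclusion.** The point holds as an unresolved overlap in the primary endpoint. The same recorded death is an event under the running text and the death row, and a censored time under a literal reading of the withdrawal row, which is also wider than the PFS definition. About 2 to 7 outcomes (5% to 15% of 48) could depend on the choice. This rests on the plan's drop-out rate with exponential times, and on an assumed 25% to 75% of leavers having a recorded death within 18 weeks.

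With equal exits the HR differs by only about 0.01 to 0.03 between the readings. With unequal exits the bias could go either way. The trial is exploratory, with one-sided alpha 0.15, which limits the weight of the point. The primary event definition should still be unambiguous before the analysis is run.

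**What to change.** In SAP 7.1.1 and 7.3:

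1. Replace the withdrawal row with: *Withdrawal of consent or loss to follow-up, with no progression or death recorded by the data cut-off: censored at last evaluable scan.*
2. State that the death row takes precedence for any recorded death within the existing 18-week limit, including after treatment or study discontinuation, where the data may be used under the subject's consent.
3. Add a sensitivity analysis that applies the alternative handling, censoring these subjects at withdrawal.

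The cost is two row edits and one extra run of the planned log-rank and Cox analyses. No new data are needed, because deaths are already collected for OS. The sample size, alpha and the 48-event target do not change. The small downside is that a few subjects move from censored to event compared with a literal reading of the present row.
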